Steady-state exposures (AUC from 0 to 24 hours [AUC₀₋₂₄]) in rats at the lowest dose (100 mg/kg/day) at which no CCI occurred in the 13-week adolescent rat study were 2.5- to 8-fold greater than that observed in humans at the recommended Phase 2 dose (RP2D; 800 mg twice daily [BID]) from the ongoing Phase 1/2 Study E7438-G000-101. In male juvenile rats, CCI was not seen at 50 mg/kg/day (AUC_(0-24h)=6340 ng•h/mL). A low incidence of CCI (2/60) was seen at AUC_(0-24h) 18,500-67,200 ng-h/mL and greater for juvenile rats, with higher incidence at AUC_(0-24h) 125,000- 290,000 ng-h/mL The first incidence of CCI in juvenile rats occurred at a similar AUC_{0-24h} as the single pediatric patient that developed CCI on Study EZH-102. There have been no cases of CCI in any adult patient given tazemetostat.

All patients will be actively monitored for signs or symptoms of abnormal bone formation during the trial. No incidences of new abnormal bone formation have been observed in the ongoing clinical study.

Female subjects of reproductive age will provide blood and urine samples for pregnancy testing at screening. All subjects must agree to use a reliable birth control method during and after the study as described in Section 8.5.11.

Additional animal toxicology is provided in the Investigator's Brochure (IB) for tazemetostat.

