Based on the nonclinical toxicology of tazemetostat, the potential risks associated with treatment include CCI, bone changes, bile duct hyperplasia, lymphoid depletion, teratogenicity, and phototoxicity.

As per Section 1.6.2, there is a potential risk of bromide toxicity related to the hydrobromide salt used in the formulation of tazemetostat. Signs of bromide toxicity consist of CNS AEs including

lethargy, headache, ataxia, and coma. As described in Section 1.4.2 (clinical experience), bromide elevation was reported in 3 (3.3%) of 90 pediatric subjects as of 24 May 2019, all of which were considered to be related to tazemetostat treatment, but there were no AEs suggestive or indicative of bromide toxicity.

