8.1 Schedule of Assessments and Procedures

Table 11. Schedule of Assessments and Procedures

Phase	Pre-treatment ^a	Treatment						Post-Treatment/Early Termination ^w	Follow-up ^{x,y}
Period	Screening ^b	Cycle 1 (Weeks 1-4) (± 1 day)				Cycles 2 and Beyond (± 3 days)		(± 3 days)	
Visit	1	2	3	4	5	6, 8, etc.	7, 9, etc.	97	98
Day	-14 ^b to -1	1	8	15	22	Day 1 of cycle	Day 15 of cycle		
Procedures/Assessments									
Informed consent	X								
Inclusion/exclusion criteria	X								
Demographics ^c	X								
Medical History/Current Medical Conditions ^d	X	X	X	X	X	X		X	
Prior and Concomitant Medications	Throughout the study								
Physical examination - Complete	X	X				X		X	
Physical examination - Symptom directed			X	X	X		X		
Focused neurologic history and examination		X	X	X	X	X	X	X	
Weight	X	X	X	X	X	X	X	X	
Height	X	X				X		X	
BSA ^e		X				X			
Vital signs ^f	X	X	X	X	X	X	X	X	
Performance Status ^g	X	X				X		X	
12-lead ECGs ^h	X	X	X	X	X	X		X	
ECHO or MUGA scan ⁱ	X							X	
Pregnancy test ^j	X	X				X		X	
Hematology ^k	X	X	X	X	X	X	X	X	
CCI									
Blood chemistry ^k	X	X	X	X	X	X		X	

Phase	Pre-treatment ^a	Treatment							
Period	Screening ^b	Cycle 1 (Weeks 1-4) (± 1 day)				Cycles 2 and Beyond (± 3 days)		Post-Treatment/Early Termination ^w (± 3 days)	Follow-up ^{x,y}
Visit	1	2	3	4	5	6, 8, etc.	7, 9, etc.	97	98
Day	-14 ^b to -1	1	8	15	22	Day 1 of cycle	Day 15 of cycle		
Coagulation Profile ^l	X					X ^l		X	
Bromide level		X (pre-dose)				X		X	
Urinalysis	X	X				X		X	
Creatinine clearance ^m	X								
PGx blood sample ⁿ	X								
PK blood samples ^{o,z}						X ^{o,z}			
PK CSF samples ^p	X					X ^p			
CCI									
Bone monitoring ^r	X					X (every 24 weeks)			
CCI									
Tumor assessments: CT, MRI, bone scan, brain scan ^{u, v, x, z}	X ^b	Tumor assessments must be performed every 8 weeks from start of dosing							X ^x
Optional chest ultrasound ^{aa}	X	Every 8 weeks from start of dosing whilst subject is receiving study drug							
¹⁸ FDG-PET scan ^v		If clinically indicated							
AEs/SAEs/AESIs ^z		Throughout study							
Tazemetostat administration		Continuous 28-day administration of oral suspension of tazemetostat BID for subjects in Cohorts 1, 2, & 3, and tazemetostat tablets TID for subjects in Cohort 4							
Survival Status and information collection ^y									X ^y
Annual Assessments ^z		X ^z							

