- o. **PK:** Blood samples for PK analysis will be collected only at annual assessments. For subjects who are undergoing disease assessment that includes CSF collection for PK (see footnote “p”), draw PK blood sample within 30 minutes of CSF sampling and both samples may be obtained between 0-8 hrs post-dose. A 1 mL blood sample will be collected at the annual time point for subjects \geq 1 year of age. A 0.5 mL blood sample will be collected at the annual time point for subjects < 1 year of age. All PK blood samples may be drawn from central venous catheter or peripheral blood draw and should be \pm 15 min from the scheduled draw time after dosing. The exact time of draw must be recorded. See Section 8.2 for window timing allowances.
- p. **CSF PK:** CSF PK samples will be collected only for subjects who require CSF sampling for disease assessment at Screening after consent is signed and at time of the first disease assessment. If a CSF sample is obtained for tumor assessment, 1 mL of CSF should be collected for CSF PK with paired blood sample for PK collected within 30 minutes of the time that the CSF sample is obtained. Both samples should be obtained between 0-8 hours post-dose
- q. **CCI**
- r. **Bone Monitoring:** Assessment of tibial growth plate, total calcium, phosphorus, magnesium, albumin will be performed during Screening or prior to dosing on Day 1 and then every 6 months while receiving study treatment.
- s. **CCI**
- t. **Tumor Biopsy:** A tumor biopsy will be requested, where medically feasible, at disease progression.
- u. **Disease Assessment:** Tumor assessments by disease-appropriate standard criteria (RECIST 1.1 or RANO) using CT, MRI of known sites of disease as clinically indicated. For subjects with bone disease or CNS disease at baseline, for cycles 1 through 12, a bone or brain scan, respectively, is required every 8 weeks or sooner, if clinically indicated. For cycles 13 and beyond, a bone or brain scan is required every 13 weeks, or sooner, as clinically indicated. Tumor assessments must be performed at Screening and every 8 weeks (\pm 3 days) from start of dosing, irrespective of treatment delays, (during Weeks 8, 16, etc.) or sooner, if clinically indicated. For subjects who stop treatment after one year of first response (CR or PR) or after one year of treatment for subjects with SD, disease assessments should be conducted every 8-12 weeks or according to institutional standards until relapse.

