8.5.1 Physical Examinations

8.5.1.1 Comprehensive Physical Examination

Comprehensive physical examinations of all body systems will be performed during Screening and at regular intervals during the study, including neurological examination.

A comprehensive physical examination will be performed at Screening and on Day 1 of each treatment cycle by a qualified licensed individual. A review of body systems will include the following:

- General appearance
- Skin
- Head, Ears, Eyes, Nose, Throat (HEENT)
- Respiratory
- Cardiovascular
- Abdomen (including liver and kidneys)
- Genitourinary
- Musculoskeletal

Any abnormalities or changes in intensity noted during the review of body systems should be documented in the source document and reported appropriately in the eCRF. If a new clinically significant finding (e.g., not noted at Screening) occurs from the initial tazemetostat administration until the end of the study, an AE must be documented. In addition, resolution of any abnormal findings during the study will be noted in source document and the eCRF if clinically significant.

Height is required at Screening, on Day 1 of each treatment cycle, and at the Post-Treatment/Early Termination visit. Weight is required at Screening, on Day 1 of each treatment cycle, and at the Post-Treatment/Early Termination visit. These assessments will be completed as indicated in the Schedule of Assessments and Procedures (Table 11).

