10.5 Other Adverse Event (OAEs)

Adverse events associated with study drug overdose, misuse, abuse, and medication error refer to AEs associated with uses of the study drug outside of that specified by the protocol. Overdose, misuse, abuse, and medication error are defined as follows:

- Overdose: Accidental or intentional use of the study drug in an amount higher than the protocol-defined dose
- Misuse: Intentional and inappropriate use of study drug not in accordance with the protocol
- Abuse: Sporadic or persistent intentional excessive use of study drug accompanied by harmful physical or psychological effects
- Medication error: Any unintentional event that causes or leads to inappropriate study drug use or subject harm while the study drug is in the control of site personnel or the subject.

All AEs associated with an overdose should be captured on the AE eCRF. Both the AEs associated with the exposure and the overdose, misuse, abuse, or medication error should be reported using the procedures for reporting SAEs (Section 10.10), even if the AE associated with overdose, misuse, abuse, or medication error does not meet serious criteria. Abuse is always to be captured as an AE. If the AE associated with an overdose, misuse, abuse, or medication error does not meet serious criteria, it must still be reported using the SAE form and in an expedited manner, but it should be noted as nonserious on the SAE form and the AE eCRF.

In addition, the following events are considered events of clinical interest (ECI) and should be reported in the same manner as SAEs, regardless of seriousness:

- Events considered related to new abnormal bone formation and confirmed by radiologic scan.
- Elevated bromide

For each serious OAE, a narrative will be written and included in the CSR.

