17.4. VITAL SIGNS

Weight (kg) and height at screening (cm), as well as vital signs for systolic blood pressure (mmHg), sitting diastolic blood pressure (mmHg), sitting heart rate (bpm), respiratory rate (breaths/min), and temperature (C°) will be collected and listed. Summaries of heart rate, temperature, systolic blood pressure, and diastolic blood pressure will be based on markedly abnormal criteria defined in **Table 6** below:

Table 6: Vital Signs Marked Abnormality Criteria

Vital Sign	Markedly Abnormal Criteria
Heart rate (bpm)	< 60 bpm > 100 bpm
Temperature (°C)	≤ 35 °C ≥ 38 °C
Systolic blood pressure (mmHg)	120-139 mmHg, inclusive (CTCAE grade 1) 140–159 mm Hg, inclusive (CTCAE grade 2) ≥ 160 mmHg (CTCAE Grade 3)
Diastolic blood pressure (mmHg)	80–89 mmHg, inclusive (CTCAE grade 1) 90–99 mm Hg, inclusive (CTCAE grade 2) ≥ 100 mmHg (CTCAE grade 3)

Incidence of markedly abnormal worst-case values will be presented. For heart rate and temperature, both high and low values will be presented separately such that subjects can be counted in both categories. Markedly abnormal vital sign values will be flagged as such on the vital signs listing.

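### The SAP plans no output for post-baseline height or growth-plate results, so a growth or bone effect would show only as an adverse event or abnormal chemistry

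*SAP*

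**What the plan says.** **The risk.** Protocol 1.6.5 includes among the potential risks drawn from nonclinical toxicology "bone changes, bile duct hyperplasia, lymphoid depletion, teratogenicity, and phototoxicity". Protocol 1.6.1 makes a commitment: "All patients will be actively monitored for signs or symptoms of abnormal bone formation during the trial". Protocol 10.5 makes one kind of bone finding an event of clinical interest, reported like a serious event whatever its seriousness: "Events considered related to new abnormal bone formation and confirmed by radiologic scan".

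**What is collected.** Protocol Table 11, footnote r: "Assessment of tibial growth plate, total calcium, phosphorus, magnesium, albumin will be performed during Screening or prior to dosing on Day 1", and then at intervals on treatment. The table row gives the interval as 24 weeks and the footnote gives it as 6 months. Protocol 8.5.1.1 states: "Height is required at Screening, on Day 1 of each treatment cycle", and again at the post-treatment visit.

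**What is to be reported.** Protocol 14.5.5 (Other Safety Measures) has scheduled physical examination and vital-sign results, among others, summarised and fully listed. SAP 17.4 gives the listing as "Weight (kg) and height at screening (cm), as well as vital signs for systolic blood pressure (mmHg" and further vital signs. Its summaries cover heart rate, temperature and blood pressure only. SAP Section 17 otherwise covers adverse events, laboratory data, ECG and ECHO/MUGA. None of its subsections mentions the growth plate or bone monitoring.

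**The concern.** The trial enrols children from 6 months to under 18 years of age, who may be treated for up to two cumulative years. Height each cycle and repeated growth-plate assessment are the two planned measurements that bear directly on skeletal growth. If the SAP is followed exactly, neither appears after baseline in any planned table or listing.

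Two things are at stake. A gradual effect is visible only in serial measurements and may never prompt an event report. A reassuring statement also needs a denominator. Protocol 1.6.1 says that no new abnormal bone formation has been seen so far; to repeat that in the study report, one must know how many children had a baseline and at least one later assessment, and no planned output gives that number. Safety and tolerability, including other safety measures, is a secondary objective for all subjects, so this part of it would be answered incompletely.

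**Working it through.** The plan states no figure to reproduce here. The check compares planned collection with planned output and then counts the scheduled measurements.

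**1. Is the material in the SAP's scope?** SAP Section 1 leaves out only PK, pharmacodynamics and exploratory endpoints. Bone monitoring and height are safety data, so they are in scope.

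**2. Collection against output.**

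| Item | Collected (Protocol) | Planned output (SAP) |
|---|---|---|
| Height | Screening, Day 1 of each cycle, post-treatment (8.5.1.1, Table 11) | Listed at screening; no summary (17.4) |
| Tibial growth plate | Baseline, then every 24 weeks (Table 11 row) or every 6 months (footnote r) | None |
| Calcium, phosphorus, magnesium, albumin | With bone monitoring, and as routine chemistry (8.5.10) | All values listed; shifts to worst value (17.2) |
| Bone event of clinical interest | Reported like an SAE (10.5) | General adverse-event tables and listings only; the special-interest table follows Protocol 10.4 (17.1) |

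**3. Is the gap declared?** Protocol 14.3.3 requires departures from its analysis plan to be documented in the SAP and the study report. SAP 3.2 lists changes to laboratory summaries, confidence levels and one subgroup analysis. It lists nothing on height or bone. Height is specified in the protocol's physical-examination section, so listing it at screening only falls short of 14.5.5. Section 14.5.5 does not name growth-plate assessment; for that item the commitment to list everything applies only on a broad reading, and otherwise both documents are silent.

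**4. How much is dropped per child?**
- Full two years: 2 × 365.25 = 730.5 days. Day 1 heights: 730.5 / 28 = 26.1, so about 26. Adding screening and post-treatment gives about 28. The SAP lists 1.
- Growth plate over the same period: 730.5 / 7 = 104.4 weeks; 104.4 / 24 = 4.3, so 4 on treatment. At 6-month intervals, 24 / 6 = 4. With baseline that is 5 under either interval. The SAP reports 0.
- A child treated for 24 weeks (168 days): 168 / 28 = 6 Day 1 heights, plus 2 = 8, of which 1 is listed. A follow-up growth-plate assessment is due under the table row, but not yet under the footnote, since 730.5 / 4 = 182.6 days. The two intervals must therefore be reconciled before the number of assessments due can be counted.

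**5. How many children?** The documents give no exposure distribution. Protocol Table 1 reports, among 85 children, 20% with stable disease (defined as at least 32 weeks) and 13% responding: 0.20 × 85 = 17, and 0.13 × 85 = 11, together 28. These counts only indicate the order of size.

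**The case against.** The strongest reply is that bone findings have several other routes into the report, and that is correct:

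- Related, scan-confirmed new bone formation is reported like an SAE (Protocol 10.5), with a narrative if serious.
- Scan or vital-sign findings judged clinically significant, or leading to an intervention, are recorded as adverse events (Protocol 10.3), and so are new clinically significant examination findings (8.5.1.1).
- SAP 17.1 tabulates treatment-emergent events by organ class and preferred term and lists all events.
- Four of the five bone-monitoring components are chemistries with planned listings and shifts (SAP 17.2).

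A reader might infer from the missing outputs that a growth or bone signal could not reach the report at all. These routes show that it could.

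The routes are selective, however. The event of clinical interest requires a judgement of relatedness and new bone formation; slowed growth does not meet it. The adverse-event route depends on a finding being judged clinically significant or leading to action. Chemistry measures neither growth nor the growth plate. None of them supplies a denominator.

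Two further replies carry some weight. First, the restriction on height may be loose drafting, since SAP 6.2.3 says that listings include scheduled and unscheduled data. But a general rule does not clearly override a specific limit, and a programmer would work from 17.4. Second, height change cannot be attributed to the drug: there is no control group, and prior craniospinal or total body irradiation and glucocorticoid use are allowed. That limits interpretation, but it is no reason to leave the data out.

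**Conclusion.** The point holds in this form: the SAP plans no listing or summary of height after screening and none of growth-plate results, and it does not declare the gap. A growth or bone effect would appear only if someone recorded it as an adverse event or if chemistry became abnormal. Gradual slowing of growth, growth-plate change not judged clinically significant, and the number of children assessed would all be lost. For a child treated for two years, 1 of about 28 scheduled heights and 0 of 5 growth-plate assessments would be shown; few children may be treated that long.

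Three stronger readings are not supported. The documents do not show that all bone signals would be hidden, for the reasons above. They do not say that the growth plate is examined by films: footnote r names no modality. And 28 children is not an upper limit on those affected, because it leaves out stable disease lasting 24 to 32 weeks and assumes that every responder reached 24 weeks.

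The conclusion assumes that SAP 17.4 is programmed as worded and that no separate document specifies these outputs. The primary response analysis is untouched. The SAP should be changed before database lock.

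**What to change.** - **SAP 17.4:** remove the limit to screening. List height at every scheduled visit and summarise change from baseline, standardised for age and sex if a growth reference is named.
- **New SAP subsection on bone monitoring:** list growth-plate results by visit, with the number of children assessed at baseline and at each later time point. Add a baseline-to-worst shift table only if result categories are collected; the documents define none.
- **SAP 17.1:** count and list the Protocol 10.5 events of new abnormal bone formation, by study part and cohort.
- **Protocol Table 11:** reconcile the interval in the row with that in footnote r, so that assessments due can be counted.
- **SAP 3.2:** if any of these outputs is deliberately left out, declare it and give the reason.

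The cost is a few tables and listings, plus a choice of growth reference if heights are standardised. Study conduct does not change, apart from settling the interval. The case report form is not among the documents, so it must be checked that growth-plate results are held in a form that can be listed. The summaries should be labelled descriptive.

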17.5. ECHO/MUGA

For ECHO/MUGA left ventricular ejection fraction, results will be listed along with the type of assessment (MUGA or echocardiogram).

APPENDIX 1. PARTIAL DATES CONVENTIONS

ALGORITHM FOR TREATMENT EMERGENCE OF ADVERSE EVENTS:

START DATE	STOP DATE	ACTION
Known	Known/Partial /Missing	If start date < study drug start date, then not TEAE If start date >= study drug start date and < (end of treatment + 30 days) or start date of new anti-cancer therapy, whichever is sooner, then TEAE If start date > (end of treatment + 30 days) start date of new anti-cancer therapy, whichever is sooner, then not TEAE
Partial, but known components show that it cannot be on or after study drug start date	Known/Partial /Missing	Not TEAE
Partial, could be on or after study drug start date	Known	If stop date < study drug start date, then not TEAE If stop date >= study drug start date, then TEAE
	Partial	Impute stop date as latest possible date (i.e. last day of month if day unknown or 31st December if day and month are unknown), then: If stop date < study drug start date, then not TEAE If stop date >= study drug start date, then TEAE
	Missing	Assumed TEAE
Missing	Known	If stop date < study drug start date, then not TEAE If stop date >= study drug start date, then TEAE
	Partial	Impute stop date as latest possible date (i.e. last day of month if day unknown or 31st December if day and month are unknown), then: If stop date < study drug start date, then not TEAE If stop date >= study drug start date, then TEAE
	Missing	Assumed TEAE

ALGORITHM FOR PRIOR / CONCOMITANT MEDICATIONS:

START DATE	STOP DATE	ACTION
Known	Known	
If stop date < study drug start date, assign as prior
 
If stop date >= study drug start date and start date <= end of treatment + 30 days, assign as concomitant
 
If stop date >= study drug start date and start date > 30 days after the end of treatment, assign as post-treatment

	Partial	
Impute stop date as latest possible date (i.e. last day of month if day unknown or 31st December if day and month are unknown), then:
 
If stop date < study drug start date, assign as prior
 
If stop date >= study drug start date and start date <= end of treatment + 30 days, assign as concomitant
 
If stop date >= study drug start date and start date > 30 days after the end of treatment, assign as post-treatment

	Missing	
If stop date is missing could never be assumed a prior medication
 
If start date <= end of treatment + 30 days, assign as concomitant
 
If start date > 30 days after the end of treatment, assign as post-treatment

Partial	Known	
Impute start date as earliest possible date (i.e. first day of month if day unknown or 1st January if day and month are unknown), then:
 
If stop date < study drug start date, assign as prior
 
If stop date >= study drug start date and start date <= end of treatment + 30 days, assign as concomitant
 
If stop date >= study drug start date and start date > 30 days after the end of treatment, assign as post-treatment

	Partial	
Impute start date as earliest possible date (i.e. first day of month if day unknown or 1st January if day and month are unknown) and impute stop date as latest possible date (i.e. last day of month if day unknown or 31st December if day and month are unknown), then:
 
If stop date < study drug start date, assign as prior
 
If stop date >= study drug start date and start date <= end of treatment + 30 days, assign as concomitant
 
If stop date >= study drug start date and start date > 30 days after the end of treatment, assign as post-treatment

START DATE	STOP DATE	ACTION
	Missing	
Impute start date as earliest possible date (i.e. first day of month if day unknown or 1st January if day and month are unknown), then:
 
If stop date is missing could never be assumed a prior medication
 
If start date \leq end of treatment + 30 days, assign as concomitant
 
If start date $>$ 30 days after the end of treatment, assign as post-treatment

Missing	Known	
If stop date $<$ study drug start date, assign as prior
 
If stop date \geq study drug start date, assign as concomitant
 
Cannot be assigned as post-treatment

	Partial	
Impute stop date as latest possible date (i.e. last day of month if day unknown or 31st December if day and month are unknown), then:
 
If stop date $<$ study drug start date, assign as prior
 
If stop date \geq study drug start date, assign as concomitant
 
Cannot be assigned as post-treatment

	Missing	Assign as concomitant

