- v. **Disease Assessment:** 18 F-DG-PET scan to be performed if clinically indicated at the Investigator’s discretion. It is not a required disease assessment.
- w. **Post-Treatment/Early Termination Visit:** A Post-Treatment/Early Termination visit will be conducted within 30 days (\pm 3 days) after last dose of tazemetostat; prior to the start of a new treatment or therapy; or if the subject's participation is terminated early. This may occur at the time of treatment discontinuation (e.g., at the visit at which the decision to discontinue treatment occurs) or up to 30 days after the final dose of study drug. AE and concomitant medication data must be collected for 30 days after the final dose of study drug, or until the start of new therapy. If subject is unable to return to the clinic for assessment of AEs this may be done by telephone as long as the study subject does not require laboratory and/or other assessments related to any new or ongoing AEs, in which case a clinical visit will be required. In the event of a continuing AE, the subject will be asked to return for follow-up until the AE has resolved or is deemed to be continuing indefinitely.
- x. **Follow-Up for Progression-Free Survival:** Subjects who discontinue study treatment for reasons other than disease progression will continue to have disease assessments, when possible, every 8 weeks until disease progression or death.
- y. **Follow-Up for Overall Survival:** Subjects who permanently discontinue study treatment will be followed (by phone, email, or clinic visit) for survival every 16 weeks until death, withdrawal of consent, or they are lost to follow-up. Survival follow-up will continue for 2 years for each subject or until 80% of subjects enrolled have died. All anticancer therapies will be collected (the Sponsor may choose to stop the collection of therapies after the first anticancer treatment). Additionally, AESI and subsequent anti-cancer therapy information will be collected throughout the survival follow up.

- z. **Annual Assessments:** Annual assessments will be conducted including to review for AEs of special interest, tumor response if PD has not been previously reported, and PK (see footnote “o”).
- aa. **Optional Chest Ultrasound:** An optional chest ultrasound may be performed at the Investigator’s discretion to monitor for early signs of CCI/T-ALL.

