The completion of the primary endpoint of the study is expected to occur approximately 6 months after the date the last subject is enrolled to treatment and evaluated for response. The end of study will occur when the last subject discontinues the study treatment and has had the opportunity to complete the safety follow-up visit (30 days after last dose of tazemetostat) or the long-term survival follow-up period (2 years from first dose of tazemetostat), whichever is later. The study may end prior to this if 80% of enrolled subjects are deceased prior to the collection of the last survival follow-up.

Survival follow-up will continue for 2 years for each subject or until 80% of treated subjects have died.

All patients are to discontinue participation on the study after 2 years of cumulative treatment, regardless of whether they came off study due to clinical response or if they reduced dose.

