17.1. ADVERSE EVENTS

Verbatim AEs terms will be coded using the Medical Dictionary for Regulatory Activities (MedDRA) version in effect at the time of the analysis. Summary tables will be based on treatment emergent adverse events (TEAEs) which are defined as AEs that started or worsened

in severity on or after the day of the first dose of study drug through 30 days after the end of study drug. Missing or partially missing start and end dates for AEs and SAEs will be handled according to the conventions described in Appendix A. For cases in which it is not possible to ascertain treatment-emergence, the event will be classified as treatment-emergent. All AEs, treatment emergent or otherwise, will be presented in subject data listings.

Each summary table will include the incidence (number and percentage) of subjects reporting any TEAE, as well as, by SOC and PT. A subject will be counted once within an SOC, even if the subject experienced more than one TEAE within a specific SOC (likewise for PT).

Investigator assessed severity grade will be based on the National Cancer Institute CTCAE, version 4.03. For summary purposes, TEAEs with a missing severity will be classified as missing. A subject will be counted once at the worst severity grade within a SOC and/or PT.

Investigator assessed causality to study drug will be categorized as “not related,” “unlikely related,” “possibly related,” or “related” to study drug. For summary purposes, treatment-related TEAEs will include events with relationship to study drug classified as “possibly related” or “related”. A TEAE with a missing causality will be classified as “possibly related” to study drug. A subject will be counted once at the strongest causality within a SOC and/or PT.

TEAEs of special interest are defined in Section 10.4 of the protocol. In consultation with study clinicians, this subset of TEAEs will be identified using MedDRA terms.

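### SAP Appendix 1 does not implement the treatment-emergence window of SAP 17.1: boundary days have no class, partly dated late events have no upper limit, and only the appendix stops at new therapy

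*SAP*

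**What the plan says.** SAP 17.1 defines TEAEs as events that start or worsen "on or after the day of the first dose of study drug through 30 days after the end of study drug". Day 30 is inside the window, and new anti-cancer therapy is not mentioned. The section refers missing and incomplete dates to an appendix (cited as Appendix A; the rules are in Appendix 1) and adds a fallback: "For cases in which it is not possible to ascertain treatment-emergence, the event will be classified as treatment-emergent".

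Appendix 1 has three relevant sets of rules.

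- **Known start date.** TEAE if "start date >= study drug start date and < (end of treatment + 30 days", or before new anti-cancer therapy if that is sooner. The opposite branch reads "If start date > (end of treatment + 30 days) start date of new anti-cancer therapy, whichever is sooner, then not TEAE". A conjunction is evidently missing there; I read it as the same cut-off.
- **Partial start date.** The only row that excludes on the start date alone is "Partial, but known components show that it cannot be on or after study drug start date". Otherwise the stop date decides: "If stop date >= study drug start date, then TEAE". With no stop date, the event is assumed TEAE.
- **Missing start date.** The same stop-date test, or assumed TEAE.

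Protocol 14.5.3 also treats incompletely dated events as TEAE unless they can be shown to precede the first dose. It sets no upper limit.

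**The concern.** A definition and the algorithm that implements it should give the same answer for every event. Here they can differ in three places: on the boundary days, for partial dates after the window, and after the start of new therapy.

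The boundary day is a plausible onset date. SAP 3.1 describes the end of study in terms of the opportunity to "complete the safety follow-up visit (30 days after last dose of tazemetostat", so a finding first seen at that visit could be dated day 30.

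The partial-date rule matters because some events are collected well after the window. Protocol 9.4 collects adverse events of special interest (AESIs) throughout survival follow-up. Protocol 10.9 keeps related serious events reportable up to any follow-up contact, and secondary lymphoma beyond 30 days. SAP 17.1 plans separate tables for TEAEs of special interest and for treatment-emergent serious events. Whether a late case enters those tables would depend on how completely its date was recorded. With few such events expected, one case would be visible.

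**Working it through.** No sample size or error rate is involved. The check applies the two rules literally to the same dates.

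**Rules.** Let S0 be the study drug start, E the end of treatment, A the event start, and C the earlier of E + 30 days and the start of new anti-cancer therapy.

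- SAP 17.1: TEAE if S0 ≤ A ≤ E + 30.
- Appendix 1, known A: TEAE if S0 ≤ A < C; not TEAE if A < S0 or A > C. The case A = C has no branch.
- Appendix 1, partial A that could be on or after S0: TEAE if the stop date is on or after S0 or is missing. C is not used.

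**Step 1: known start date, no new therapy (C = E + 30).**

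| Start, days after E | Appendix 1 | SAP 17.1 |
|---|---|---|
| 28 | TEAE | TEAE |
| 29 | TEAE | TEAE |
| 30 | no class | TEAE |
| 31 | not TEAE | not TEAE |
| 32 | not TEAE | not TEAE |

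**Step 2: known start date, new therapy on day 12 (illustration; C = E + 12).**

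| Start, days after E | Appendix 1 | SAP 17.1 |
|---|---|---|
| 11 | TEAE | TEAE |
| 12 | no class | TEAE |
| 13 | not TEAE | TEAE |

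Day 13 is an explicit disagreement, not a gap.

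**Step 3: partial start date (illustration).** Take E = 1 March 2019, so the window closes on 31 March 2019, and an event recorded as starting in September 2019. Its earliest possible start is 1 September 2019: 31 + 30 + 31 + 30 + 31 + 31 = 184 days after E, beyond day 30. Appendix 1 gives TEAE, because the month is after S0 and nothing tests the upper end. SAP 17.1 gives not TEAE. Recorded as 1 September 2019, the same event goes to the known-date row and is not TEAE.

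**Step 4: the medication table in the same appendix.** It uses ≤ at end of treatment + 30 days and > beyond it, so no day is unclassified. For partial start dates it imputes the earliest possible date and tests that against the 30-day limit. It is a model for Steps 1 and 3, but not for Step 2, since it has no new-therapy cut-off.

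**Step 5: after correction.** With ≤ in the TEAE branch, day 30 becomes TEAE, day 31 onward stays not TEAE, and no known date is unclassified when there is no new therapy. With an upper-limit test on the earliest possible start, the September 2019 event becomes not TEAE (184 > 30). Changing the inequality does nothing for day 13 in Step 2; that needs one new-therapy rule in both places.

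**The case against.** **Day 30 is an omission that 17.1 already resolves.** This largely stands. Section 17.1 sends only incomplete dates to the appendix, so a fully dated day-30 event is governed by the definition and is TEAE. A reader might infer that the SAP excludes day-30 events from the TEAE tables. It does not: the excluding branch requires a later date. What remains is a table with a missing case. The fallback in 17.1 does not clearly fill it, because emergence can be ascertained when the date is known.

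**The partial-date rule is the protocol's own and is conservative.** Both are true: Protocol 14.5.3 has no upper limit, and the rule over-counts rather than hides events. But SAP 17.1 adopted a 30-day limit and Appendix 1 applies it to known dates only. When the known date parts place the start after the window, nothing is uncertain and there is nothing to be conservative about.

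**The reach is narrow.** This stands. Routine collection stops at 30 days or at new therapy, whichever is earlier (Protocol 10.9). AESIs and serious events are reported within 24 hours of awareness, which should make vague dates uncommon. Protocol 10.2 keeps laboratory abnormalities needing no medical intervention out of the adverse event record. The laboratory and QTcF summaries use worst post-baseline values without a stated TEAE window. All adverse events are listed, whether treatment-emergent or not.

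**A frequency cannot be attached.** A reader might take the ±3-day visit window as days 27 to 33 and conclude that 1 visit in 7 falls on day 30. Protocol Table 11, footnote w, does not support that. The visit may take place when treatment is discontinued "or up to 30 days after the final dose of study drug", and is due before any new therapy. A share of visits would in any case not be a share of adverse events.

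**Conclusion.** The point holds as an inconsistency within the SAP, with small impact. Read literally, Appendix 1 leaves two boundary days without a class. It classes some partly dated events as TEAE that 17.1 would exclude, and it excludes fully dated events after new therapy that 17.1 would include.

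The partial-date rule is the most consequential part, because it makes the class of a late AESI or related serious event depend on the completeness of its date. The new-therapy mismatch reaches much the same events, since routine collection has ended by then.

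The number of events affected cannot be derived from the documents; I expect it to be small. Dose-limiting toxicities are confined to Cycle 1 and response rate does not use the TEAE flag, so neither primary analysis is affected. The conclusion assumes that end of treatment in Appendix 1 and end of study drug in 17.1 mean the same date.

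**What to change.** 1. In the known-date TEAE branch of Appendix 1, use ≤ at end of treatment + 30 days.
2. Decide whether new anti-cancer therapy closes the window. State the rule identically in SAP 17.1 and Appendix 1, assign the day of new therapy to one class, and repair the incomplete sentence in the not-TEAE branch.
3. For partial start dates, impute the earliest possible start, as the medication table does, and class the event as not TEAE if that date falls after the window. Keep completely missing start dates as TEAE unless the stop date precedes the first dose; they have no date parts to test.
4. List the departure from Protocol 14.5.3 in SAP 3.2, and correct the cross-reference from Appendix A to Appendix 1.

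The cost is one sentence in 17.1, a few rows of one table and one entry in SAP 3.2. Protocol 14.3.3 lets such deviations be documented in the SAP and the study report, and no new data are needed. The edits should be settled before the safety tables are programmed.
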